In addition to the symptoms of PTSD, several problems are frequently comorbid with PTSD. Among these, one prominent problem associated with significant medical morbidity is cigarette smoking. Many veterans with PTSD smoke cigarettes. Epidemiological data indicate that 45% of those with PTSD smoke cigarettes (Lasser, et al., 2000). Although smoking is prevalent in veterans with PTSD, many report interest in quitting smoking, with one recent study indicating that, at the time of assessment, 50% of smokers were contemplating quitting smoking and another 21% were preparing to make a quit attempt (Kirby, et al., 2008). Approaches to improving care and access to care for smokers with PTSD may be particularly useful considering the tendency for psychiatric groups to be socially isolated (Schroeder, 2008) and undertreated for smoking cessation (Prochaska & Velicer, 2004). By integrating smoking cessation interventions with mental health treatment, a greater proportion of those with psychiatric illness will receive treatment and quit smoking. In addition, research suggests that PTSD symptoms are related to smoking behavior ([name], et al., 2005).

Despite this connection, interventions seeking to assist people with PTSD in smoking cessation have not traditionally targeted PTSD symptom reduction. Integration of smoking cessation with PTSD treatment could reduce symptoms and provide patients with strategies for managing symptoms without using cigarettes.

In order to adequately examine the unique effects of CPT-C combined with integrated smoking cessation care, we will utilize a randomized controlled trial design. Both interventions will employ extensive smoking cessation treatment, including counseling, pharmacotherapy, and text messaging (described below) to assist in the quit attempt. One group will be randomized to receive CPT-C alongside the smoking cessation intervention. The other group will be offered to have 12 sessions of CPC-C post participation in the active smoking cessation portion of the study.

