## **Objectives:**

The primary aim of the proposed study is to evaluate the integration of CPT-C and smoking cessation treatment in an individual 12-session PTSD protocol as compared to a protocol including the same smoking cessation treatment for individuals with PTSD, but without CPT-C. This intervention will be evaluated with the following hypotheses:

- Compared to the smoking cessation alone protocol, the smoking cessation + concurrent CPT-C protocol will result in reduced frequency and intensity of PTSD symptoms.
- 2) Compared to the smoking cessation alone protocol, the smoking cessation + concurrent CPT-C protocol will result in reduced depressive symptoms.
- 3) The smoking cessation + concurrent CPT-C protocol will result in decreased smoking rates, relative to published data on VA smoking cessation usual care.
- 4) Greater PTSD symptom reduction during the smoking cessation + concurrent CPT-C treatment will result in longer duration to smoking lapse and relapse.
- 5) Exploratory research question: Will use of automated text messaging as an adjunct to smoking cessation be feasible, and will it impact quit rates?

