#### Intervention Protocol

If screened potential participants are deemed eligible to participate in the study, participants will be randomized to participate in either a 12-session CPT-C with concurrent smoking cessation treatment or a smoking cessation treatment including 6 individual smoking counseling sessions, to be followed (if desired) by CPT-C six months after the quit date. Both arms of the study will include text messaging to support the quit attempt (smokefree VET), pharmacotherapy for smoking cessation, and brief monthly follow-up phone contacts by therapists to support the quit attempt. The complete randomization sequence will be generated a priori and performed centrally by the study staff.

Although participants will attend a total of 15 sessions for this study, not all study sessions will include therapy. In the CPT-C and smoking condition, participants will receive 12 sessions of combined PTSD and smoking therapy. The first 50 minutes of each session will be devoted to the randomized therapy and the last 25 minutes will be devoted to the manualized integrated smoking cessation treatment by McFall and Saxon (McFall & Saxon, 2005). Sessions 7 through 12 of the treatment sessions will include 50 minutes of the randomized therapy, and brief (five to ten minutes) check-in regarding smoking relapse prevention and/or renewed quit attempts. In the smoking cessation without concurrent CPT-C condition, there will still be 15 total study sessions, with 6

including therapy for smoking cessation and lasting 25 minutes. If, during the course of treatment, a participant is lost to contact, the study coordinator will send an IRB-approved "no-contact letter" to increase the likelihood that we re-establish contact.

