# **Data Analysis and Hypotheses:**

The following variables will be described for the sample as a whole: minority status, marital status, age, trauma exposure, negative affect level, PTSD symptom severity, nicotine dependence, mean pack years, nicotine cigarette brand, and mean number of cigarettes smoked daily.

Because one of the aims of this study is to assess the efficacy of the combined CPT-C and smoking intervention on smoking cessation, we will analyze these variables to determine whether they change over time.

- Compared to the smoking cessation alone protocol, the smoking cessation + concurrent CPT-C protocol will result in reduced frequency and intensity of PTSD symptoms.
- Compared to the smoking cessation alone protocol, the smoking cessation + concurrent CPT-C protocol will result in reduced depressive symptoms.
- 3) The smoking cessation + concurrent CPT-C protocol will result in decreased smoking rates, relative to published data on VA smoking cessation usual care.
- 4) Greater PTSD symptom reduction during the smoking cessation + concurrent CPT-C treatment will result in longer duration to smoking lapse and relapse.
- 5) Exploratory research question: Will use of automated text messaging as an adjunct to smoking cessation be feasible, and will it impact quit rates and symptom severity?

Hypothesis 1. Compared to the PTSD Coach and smoking cessation protocol, the CPT-C and smoking cessation protocol will result in reduced frequency and intensity of PTSD symptoms. The change in PTSD symptoms over time will be analyzed using repeated-measures ANOVA, utilizing data provided at baseline, post-treatment, and 6-months post-quit. We will evaluate the potential influence of several potential psychosocial covariates on smoking abstinence, including: 1) demographics (age, race, socioeconomic

status), 2) psychiatric variables (PTSD symptom severity, depression, substance abuse/dependence), 3) smoking variables (self-efficacy, motivation to quit, social support, smokers in social group), and 4) treatment process variables (therapeutic alliance, satisfaction with treatment, attendance at sessions, homework adherence).

Hypothesis 2. Compared to the PTSD Coach and smoking cessation protocol, the CPT-C and smoking cessation protocol will result in reduced depressive symptoms. Analysis procedures for Hypothesis 2 will be the same as those used for Hypothesis 1.

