Hypothesis 3. The CPT-C and smoking cessation protocol will result in decreased smoking rates, relative to published data on VA smoking cessation usual care. An outcome variable denoting the proportion of subjects abstinent at Week-6 will be regressed on the group proxy and included covariates using standard logistic regression procedures. A secondary analysis will explore cessation rates at the 6-month follow-up.

Hypothesis 4.-The level of PTSD symptom reduction during the intervention will be related to longer latency to relapse. PTSD symptom change scores will be used to evaluate the degree of PTSD symptom reduction. We will fit Cox proportional hazard regression models to the data to evaluate effects of PTSD symptom reduction on the time to relapse.

Hypothesis 5. Exploratory research question: Will use of automated text messaging as an adjunct to smoking cessation be feasible, and will it impact quit rates and symptom severity? This will be evaluated by examining proportion of participants choosing to utilize text messaging, retention rates, and usage rates.

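### Hypothesis 3 is worded against published VA usual care, but its only stated test is a regression on an undefined group variable in a trial with no usual-care arm

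*Combined protocol and SAP*

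**What the plan says.** The Objectives state H3 as "The smoking cessation + concurrent CPT-C protocol will result in decreased smoking rates, relative to published data on VA smoking cessation usual care". The hypothesis list in Data Analysis and Hypotheses repeats it, and the H3 analysis paragraph gives it a third time: "The CPT-C and smoking cessation protocol will result in decreased smoking rates, relative to published data on VA smoking cessation usual care". In both hypothesis lists, H1 and H2 are set against the smoking-cessation-alone protocol, so the lists distinguish the two comparators.

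The H3 paragraph then gives one inferential method: "the proportion of subjects abstinent at Week-6 will be regressed on the group proxy and included covariates using standard logistic regression procedures". The term *group proxy* occurs only there and is not defined. For the later time point the plan says only "A secondary analysis will explore cessation rates at the 6-month follow-up".

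On design, the Background says "Both interventions will employ extensive smoking cessation treatment, including counseling, pharmacotherapy, and text messaging". The primary aim evaluates the combined treatment "as compared to a protocol including the same smoking cessation treatment for individuals with PTSD, but without CPT-C". Under Intervention Protocol, "participants will be randomized to participate in either a 12-session CPT-C with concurrent smoking cessation treatment or a smoking cessation treatment". The analysis section also gives as an aim to "assess the efficacy of the combined CPT-C and smoking intervention on smoking cessation".

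**The concern.** The hypothesis and its test name different comparators. H3 is the only hypothesis that claims a treatment effect on smoking against a comparator: H4 relates symptom change to time to relapse, and item 5 is an exploratory question about text messaging. The trial's conclusion on smoking therefore depends on whether an analyst follows the hypothesis sentence or the analysis sentence.

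If the hypothesis sentence is followed, the benchmark could be chosen after the abstinence data are seen. A favourable result could also be credited to CPT-C when it may reflect the counselling, medication and text messaging that both arms receive. If the analysis sentence is followed, H3 as worded has no test.

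**Working it through.** **No figure to reproduce.** The documents give no abstinence rates, benchmark, significance level, power or allocation ratio. The finding comes from setting the passages side by side; the arithmetic only illustrates it.

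**Two readings of the group variable**

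| Reading | What the regression estimates | Does it test H3? |
|---|---|---|
| Randomised arm | Effect on Week-6 abstinence of adding CPT-C to the shared cessation treatment | No. The comparator is cessation alone, not usual care |
| Trial arm versus published usual care | Difference from an external rate | Not as specified. No rate, source, time point or method is given, and covariate adjustment would normally need individual external records |

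**Inputs, all assumed except the totals.** Arm sizes of 25 and 35 come from the totals of fifty and seventy in the Population section, taken as numbers randomised and split 1:1. Usual-care rates are set at 5% to 20%.

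**Illustration 1: no difference between arms, 8/35 in each.**
- Odds ratio = (8/27)/(8/27) = 1.00. SE of log OR = √(1/8 + 1/27 + 1/8 + 1/27) = 0.569. The 95% CI is exp(±1.96 × 0.569) = 0.33 to 3.05.
- One-sided exact binomial P(X ≥ 8 | n = 35, p0) for p0 = 5%, 10%, 15%, 20%: 0.0003, 0.020, 0.14, 0.40.

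**Illustration 2: CPT-C arm ahead, 12/35 versus 8/35.**
- OR = (12/23)/(8/27) = 1.76. SE = √(1/12 + 1/23 + 1/8 + 1/27) = 0.537. The 95% CI is 0.61 to 5.05.
- P(X ≥ 12 | n = 35, p0) for p0 = 10%, 15%, 20%: 0.0001, 0.004, 0.034.

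So the two questions can give different answers even when the arms differ.

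**Illustration 3: uncertainty in the benchmark.** For 8/35 against 10%, p = 0.020 if the rate is treated as fixed. If the 10% came from 10/100, 20/200 or 50/500, one-sided Fisher p = 0.055, 0.036 or 0.026.

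**Illustration 4: how far the choice of benchmark matters.** The smallest abstinent count with P(X ≥ r | p0) ≤ 0.025 rises from 6 to 13 of 35, or from 5 to 10 of 25, as p0 goes from 5% to 20%.

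**Illustration 5: H3 true, arms equal.** If both arms truly reach 30% and usual care is 10%, a one-sample exact test at one-sided 2.5% detects the difference with probability 0.66 (n = 25) or 0.87 (n = 35). A between-arm score test favours CPT-C only 2.5% to 2.7% of the time, which is its false-positive rate.

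**Power of the between-arm test, 25% versus 45%, two-sided 5%.** z = [0.20 − 1.96√(2 × 0.35 × 0.65/n)] / √[(0.45 × 0.55 + 0.25 × 0.75)/n].
- n = 25 per arm: (0.20 − 0.264)/0.132 = −0.49, power 31%.
- n = 35 per arm: (0.20 − 0.223)/0.111 = −0.21, power 42%.
- Fisher's exact test: 23% and 34%.

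**The case against.** The strongest reply is that in a two-arm trial a group variable plainly means arm. The regression is then a valid randomised comparison, matches the contrast in the primary aim, and has a model and a time point. Usual care may have been meant only as context. Most of this stands, and it limits the severity: data collection and randomisation are unaffected, and much of the repair is rewording. It does not remove the mismatch. H3 is a directional hypothesis stated three times against usual care, only item 5 is labelled exploratory, and nothing calls the comparison descriptive. Nor are the section's arm labels a safe guide: the H1 and H2 paragraphs name a PTSD Coach protocol that is not a trial arm.

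A reader might infer four stronger points that the documents do not support.
- *That all 14 listed covariates enter the H3 model.* The list sits under H1 and proposes to evaluate their influence on abstinence. The H3 paragraph refers only to included covariates, without naming them.
- *That the arms differ by design in session count, 12 versus 6.* Intervention Protocol gives six smoking therapy sessions in the control arm. Procedures gives 12 counselling sessions in each condition, and Table 2 lists smoking treatments 7 to 12 for the control arm. These passages must be reconciled.
- *That the 7- and 30-day abstinence outcomes are defective for lack of a comparator.* They appear in Assessments After Screening, which defines measurements rather than analyses.
- *That 35 per arm is settled.* Population speaks of recruiting seventy, then of recruiting 120 to enrol at least fifty. If recruit means the same in both places, seventy would yield about 70 × 50/120 ≈ 29 enrolled in total.

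**Conclusion.** The concern holds as a mismatch between hypothesis and analysis that should be fixed. Followed as written, on the natural reading, the plan tests what CPT-C adds to cessation treatment and leaves H3 untested. On the other reading, the benchmark and the method are missing. A null arm coefficient would say nothing about superiority to usual care, and a positive one would not establish it.

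This conclusion rests on the text alone. The numerical illustrations depend on assumed rates, 1:1 allocation and 50 to 70 randomised; they show that the two questions can diverge, not that they will. A reader might go further and infer that the regression is invalid, or that a benchmark has been picked after the fact. Neither is supported: as an arm comparison the regression is sound, and the plan merely leaves the benchmark open.

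**What to change.** 1. In the H3 analysis paragraph, define the group variable as randomised arm.
2. Restate H3 in all three places as the between-arm comparison of Week-6 abstinence, reported as an odds ratio with 95% CI. Report published usual care only as a descriptive benchmark, and draw no claim about CPT-C's own effect from it.
3. If the sponsor prefers to keep the usual-care claim, add it as a separate, explicitly non-randomised one-sample or historical-control comparison for the CPT-C arm. Fix its source, rate and uncertainty, time point and abstinence definition before outcome data are examined.
4. Under either route, state what counts as abstinent at Week-6 and the origin of the six weeks. The quit date is the likely origin, since nicotine replacement ends six weeks after it and Table 2 places that at session 13. Intervention Protocol allows earlier quit dates, so say which assessment counts for those participants.
5. Apply the same comparator to the 6-month analysis and name its method.
6. Name the covariates, and do not adjust the arm effect for alliance, satisfaction, attendance or homework adherence, which arise after randomisation.

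**Cost.** This is a text amendment with no new measurements. Intervention Protocol reports experience of participants wanting to quit early, which suggests that some had already been treated. The amendment should therefore be dated, and labelled if made after abstinence data were examined.

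The between-arm route gives up an inferential claim for the package and accepts the low power shown above: 23% to 34% by Fisher's exact test, for 25% versus 45%. The usual-care route has no randomised control, and its power depends on the benchmark. By exact calculation at one-sided 2.5%, for 25 and 35 in the CPT-C arm, it is 97% and over 99% for a true 45% against a fixed 10%, and 76% and 87% against 20%. For a true 25% it is 44% and 68% against 10%, and 7% and 8% against 20%.

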## Summary of Inclusion Exclusion Criteria

To be enrolled in this study, participants must have the following characteristics:

- Veteran
- Be current cigarette smokers of at least ten cigarettes a day.
- Meet criteria for current PTSD.
- Speak and write fluent conversational English.
- Be between 18 and 75 years of age.
- Be willing to attempt smoking cessation.

Potential participants will be excluded from participating in this study for the following reasons:

- Screened participants will not be stable on their medications for the study period
- Screened participants who have a history of myocardial infarction in the past 6 months
- Screened participants who have a contraindication to NRT and are unable to get medical clearance from their primary care provider will be excluded.

- Screened participants who use any other forms of tobacco such as cigars, pipes, or chewing tobacco and are unwilling to stop using.
- Pregnancy
- Inability to complete study measures and tasks independently
- Dementia or other brain disorder, schizophrenia, current manic syndrome, or substance abuse/dependence in the preceding 3 months.
- Currently receiving trauma-focused psychotherapy.
- Currently enrolled in another smoking cessation trial.
- Currently living in court-ordered residential substance abuse treatment.

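### Hypothesis 4 relates a PTSD change score to time to relapse without specifying adjustment for baseline PTSD severity, so its hazard ratio can be confounded and may be diluted

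*Combined protocol and SAP*

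**What the plan says.** The Hypothesis 4 paragraph under Data Analysis and Hypotheses defines the exposure and the model in two sentences: "PTSD symptom change scores will be used to evaluate the degree of PTSD symptom reduction" and "We will fit Cox proportional hazard regression models to the data to evaluate effects of PTSD symptom reduction on the time to relapse". It does not name the instrument, the two time points of the change, or any covariate. The numbered hypothesis is worded for the combined-treatment arm: "Greater PTSD symptom reduction during the smoking cessation + concurrent CPT-C treatment will result in longer duration to smoking lapse and relapse".

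Covariates appear in two neighbouring places. Under Hypothesis 1 the plan states: "We will evaluate the potential influence of several potential psychosocial covariates on smoking abstinence", and the list includes "psychiatric variables (PTSD symptom severity, depression, substance abuse/dependence". That text does not call the severity score a baseline score and does not mention the Cox model. Under Hypothesis 3 the abstinence outcome is to be "regressed on the group proxy and included covariates using standard logistic regression procedures". Hypothesis 4 has no such phrase.

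Two other statements bear on the point. Entry requires that participants "Meet criteria for current PTSD", and the Background says that "research suggests that PTSD symptoms are related to smoking behavior". The CAPS and the PCL are both collected at screening. The CAPS is repeated at session 14, and the quit date is scheduled for session 7.

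**The concern.** A reduction score is the baseline score minus a later score, so it carries the baseline score inside it. Patients who start higher have more room to fall and regress further. If baseline severity also raises the risk of relapse, the largest reductions occur disproportionately in patients at higher relapse risk. A Cox coefficient for change alone then mixes a protective effect of improvement with a harmful effect of where the patient started.

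Hypothesis 4 is the only listed hypothesis that tests whether PTSD improvement prolongs time to relapse, which is the rationale the Background gives for integrating the two treatments. Someone following its paragraph literally would fit change alone, and could report little or no association when one exists.

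**Working it through.** **No figure to reproduce.** The plan gives no hazard ratio, event count, SD, pre-post correlation or power for Hypothesis 4. Every numerical input below is an assumption unless a source is named.

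**Set-up.** Let B be the baseline score, P the later score and D = B − P the reduction. Let log hazard = −β·D + γ·B, so β > 0 means that improvement protects and γ > 0 means that baseline severity independently raises the hazard. If B is left out, then approximately:

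- coefficient on D = −β + γ·k
- k = SD_B·(SD_B − ρ·SD_P) / Var(D)
- share of the true log HR kept = 1 − (γ/β)·k

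**Value of k** (in units of SD_B):

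- Equal SDs: k = (1 − ρ)/(2 − 2ρ) = 0.50 at any ρ below 1.
- SD_P/SD_B = 1.3, ρ = 0.5: k = (1 − 0.65)/(1 + 1.69 − 1.30) = 0.35/1.39 = 0.25.
- SD_P/SD_B = 1.6, ρ = 0.7: k = (1 − 1.12)/(1 + 2.56 − 2.24) = −0.12/1.32 = −0.09.
- SD_P/SD_B = 0.8, ρ = 0.5: k = (1 − 0.40)/(1 + 0.64 − 0.80) = 0.60/0.84 = 0.71.

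**A natural reference case.** If relapse depends on the symptoms a patient still has, the hazard follows P. Since β·P = −β·D + β·B, this is γ/β = 1. The share kept is then 0.50 at equal SDs, 0.75 at ratio 1.3, 1.09 at ratio 1.6 with ρ = 0.7, and 0.29 at ratio 0.8.

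**Cox fits at large sample** (40,000 simulated patients, equal SDs, ρ = 0.5, true HR 0.667 per SD of reduction, about 70% relapsing):

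| γ/β | Share kept (formula) | HR, change only |
|---|---|---|
| −0.5 | 1.25 | 0.61 |
| 0 | 1.00 | 0.67 |
| 0.5 | 0.75 | 0.74 |
| 1 | 0.50 | 0.83 |
| 2 | 0.00 | 0.99 |
| 3 | −0.50 | 1.16 |

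With B added, the HR was 0.66 to 0.68 in every row. At γ/β = 1 the formula gives exp(0.5 × ln 0.667) = 0.82, against 0.83 simulated.

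**Second set of inputs.** Take HR 0.70 per SD of reduction, HR 1.5 per SD of baseline severity, equal SDs and ρ = 0.5. The correlation of D with B is sqrt((1 − 0.5)/2) = 0.50, and ln 0.70 + 0.50 × ln 1.5 = −0.357 + 0.203 = −0.154, so the change-only HR is 0.86.

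**Power at the size of one arm.** The Population section gives seventy to be recruited and an enrolment goal of at least fifty. With equal allocation, which the protocol does not state, one arm has 35 or 25 patients. Power to detect the benefit (true HR 0.667, equal SDs, ρ = 0.5, two-sided 5%, 1,500 fits per setting):

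| n | γ/β | Change only | With baseline |
|---|---|---|---|
| 25 | 0 | 36% | 30% |
| 25 | 0.5 | 22% | 28% |
| 25 | 1 | 12% | 28% |
| 35 | 0 | 48% | 39% |
| 35 | 0.5 | 31% | 39% |
| 35 | 1 | 15% | 36% |

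About 48 relapses are needed for 80% power: (1.96 + 0.84)² / (ln 1.5)² = 7.85/0.164. At 70% relapse, one arm supplies 0.7 × 25 = 17.5 to 0.7 × 35 = 24.5.

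**Timing check.** With no true effect, but with relapse in about the first quarter of follow-up reducing the measured improvement by 0.25 to 0.5 baseline SD, the baseline-adjusted model still gave HR 0.80 to 0.90 per baseline SD of reduction.

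**The case against.** The strongest reply has four parts.

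1. **Silence is not exclusion.** The paragraph speaks of models in the plural and rules nothing out, and PTSD severity is on the Hypothesis 1 covariate list for abstinence. A reader might infer that the plan leaves baseline severity out on purpose; the text does not support that. What it supports is that the adjustment is unspecified. The list does not close the gap, because it does not say baseline and is not tied to this model.

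2. **The bias is conditional.** A reader might infer that a real benefit is bound to be diluted. That needs γ > 0 and SD_B > ρ·SD_P, and the documents fix neither. Their only support for the first is one qualitative sentence in the Background. Requiring current PTSD at entry may narrow the baseline spread, which moves k from 0.50 toward the 0.25 case or lower. Since k depends on SDs and correlation, it also depends on the instrument and window chosen. This objection stands, and it limits the claim to what can happen.

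3. **Pooled power figures would mislead.** Power for all 50 to 70 participants makes the remedy look stronger than it is, because the hypothesis as listed concerns one arm. At 25 to 35 patients the adjusted model reaches only 28% to 39% when γ/β is 0.5 or 1. This also stands: adjustment removes a distortion but does not make the test well powered.

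4. **Adjustment has a price.** If γ = 0 it costs power: 36% to 30% at n = 25, 48% to 39% at n = 35 and, for scale, 80% to 69% at n = 70. The loss is real, but it buys an estimate whose meaning does not depend on an unmodelled baseline effect.

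**Conclusion.** The point holds in conditional form. Hypothesis 4 makes the change score the only stated predictor and does not specify baseline adjustment, so its HR is confounded whenever baseline severity independently affects relapse. Under equal SDs with the hazard following the post-treatment score, about half of the true log HR is kept. Across the cases worked above, the effect can be nearly intact, diluted, exaggerated (1.25 times at γ/β = −0.5) or reversed in sign (at γ/β = 3). None of these inputs comes from the documents, so neither the direction nor the size of the bias can be asserted for this trial.

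A reader might also infer that adding baseline severity makes the Hypothesis 4 estimate unbiased. It does not. Relapse is counted from the quit date at session 7, while the post-treatment CAPS comes at session 14. If the change runs to that visit, early relapse can influence the exposure, and the timing check shows a spurious benefit surviving adjustment. That problem is separate and needs its own decision on the change window.

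The adjustment should be made: it uses data already collected, and without it the coefficient has no clear interpretation.

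**What to change.** In the Hypothesis 4 paragraph, state that the Cox model will include the screening PTSD score on the same instrument together with the change score, and that the HR for PTSD reduction will be reported conditional on baseline severity. Entering the later score with the baseline score is equivalent: −b·D + c·B = b·P + (c − b)·B, so the coefficient changes sign but the test is the same. Name the instrument and the two time points in the same sentence, since the adjustment is undefined without them. Base any power statement on the size of the combined-treatment arm.

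The cost is a sentence or two of wording, one degree of freedom, and the loss of power shown above if baseline severity has no independent effect. No new data are needed, because screening already collects both the CAPS and the PCL.
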